2.2 BACKGROUND

Opioid analgesics are prescribed for moderate to severe acute pain; however, there are contraindications, cautions, and side effects that are common with all opioids. Dependence and tolerance are also likely with regular opioid use, resulting in the current nationwide opioid epidemic. In

Alabama alone, there were 343 opioid-related overdose deaths in 2016, 124 of which were related to prescription opioids. Alabama providers have the highest prescribing rate in the country, nearly twice the national rate, per the NIH/NIDA website (<https://www.drugabuse.gov/drugs-abuse/opioids/opioid-summaries-by-state/alabama-opioid-summary>). In 2015, the Centers for Disease Control (CDC) released prescribing guidelines relating to chronic pain, and in 2018 Alabama's Blue Cross/Blue Shield insurance group limited the supply of opioids allowed to their members to 7 days (https://www.al.com/news/index.ssf/2018/03/bluecross_blueShield_changing.html).

There is currently no clinical guideline for prescribing post-operative opioid medications for functional endoscopic sinus surgery (FESS). A 2018 survey documenting prescribing patterns by 168 members of the American Rhinologic Society found that most physicians who participated prescribed, on average, 27 opioid pain pills for patients after surgery. Prior studies have been performed to help decrease the pain patient's feel after sinus surgery. Haytoglu (2016) revealed that adding non absorbable sinus packs loaded with local anesthetics such as bupivacaine achieved less pain values and improved patient satisfaction scores.

Given this current data we believe injecting patients with a long acting analgesic during the procedure will help reduce post-operative pain. If we can decrease the amount of pain patients have in the post-operative period we can theoretically decrease the number of opioid pain pills prescribed. We plan to also track the number of opioid pills consumed by patients in the post-operative period to obtain a somewhat uniform prescribing pattern within surgeons.

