4 STUDY DESIGN

4.1 OVERALL DESIGN

Opioid analgesics are prescribed for moderate to severe pain disorders; however, there are contraindications and side effects that are common to all opioids. We hypothesize using local regional anesthetic after sinus surgery will reduce pain, therefore decreasing the need for post-operative opioid consumption.

This is a Phase 4, randomized, single-blinded, single-site, parallel-assignment intervention with a primary purpose of supportive care after functional endoscopic sinus surgery (FESS). It is anticipated that 30 subjects will be enrolled in this protocol. Potential subjects will be male or female adults over the age of 18 from the United States who undergo functional endoscopic sinus surgery (FESS) under the supervision of one surgeon.

Potential participants will be approached during their regularly-scheduled clinic visit about participation in the study. If they agree to participate, they will sign an informed consent form. During the baseline visit, demographic information, medical history, concomitant medications, vital signs, height, and weight will be collected. A routine nasal endoscopy will be performed to assess the need for surgical intervention, and routine CT sinus scans will be obtained and/or reviewed.

Participants will be randomized to one of the two following groups:

- **Treatment Group (n = 15):** participants will receive 20 mL of 1.3% bupivacaine with 2 mg dexamethasone injected locally in the location for sensory nerves of the sinus cavities and face during the FESS procedure
- **Control Group (n = 15):** participants will not receive regional anesthetic during the FESS procedure

Participants will have their scheduled functional endoscopic sinus surgery procedure. After surgery, participants will be given a pain diary to record their pain score on a scale of 1-10, and a place to record their use of opioids, as well as over-the-counter non-steroid anti-inflammatories such as acetaminophen and ibuprofen. Participants will record their scores and drug use daily for 10 days post-surgery. At their first post-operative clinic visit, the diary will be reviewed, and their opioid use will also be evaluated by counting the pills left on their prescription.

Data points/variables to be collected during the study could include the following, to be ascertained from the medical record and/or patient report:

- Name
- Medical Record Number
- Age
- Gender
- Type of surgery
- Duration of surgery

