4.2 SCIENTIFIC RATIONALE FOR STUDY DESIGN

The rationale for our study deals with anesthetizing the sensory nerves of the face. The nerve distribution of the face deals with the trigeminal nerve. We plan to inject a long acting local analgesic at the infraorbital, infatrocchlear, external nasal, supraorbital, supratrochlear nerves of the face after functional endoscopic sinus surgery. The control arm will be randomly chosen for which patient will not be injected. A potential problem with the control group is that patients in the PACU will have intact facial sensation. This could alert them to the fact that they were not injected with a local analgesic and thus reinforce the need for post-operative narcotic usage.

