4.3 JUSTIFICATION FOR DOSE

The nasal cavity is innervated by sensory nerves via the trigeminal nerve. We believe using a standardized dose of bupivacaine 1.3% combined with 2mg preservative-free dexamethasone to areas on or around the nasal cavity that are innervated with sensory nerves will improve post-operative pain control results. A max amount of 20 mL will be injected into each study participant. The control group will receive no injection.

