6.2 MEASURES TO MINIMIZE BIAS: RANDOMIZATION

Subjects will be randomized 1:1 (parallel assignment) into the two treatment groups. The next subject to be randomized into a trial will receive the treatment corresponding to the next free number in the randomization schedule. The appropriate number and associated treatment for the next subject will only be allocated when entry of that subject to the randomized part of the trial has been confirmed.

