8 STUDY ASSESSMENTS AND PROCEDURES

8.1 STUDY ASSESSMENTS

Subjects over the age of 18 who are undergoing functional endoscopic sinus surgery for chronic sinusitis as part of routine clinical care will be approached to participate in the study. Subjects screened and enrolled will follow the schedule of events provided in Section 1.2. The following evaluations will be performed:

Screening/Baseline:

- Obtain written informed consent
- Obtain demographic information
- Obtain medical history
- Obtain concomitant medication information
- Obtain routine vital signs, including height and weight
- Obtain routine nasal endoscopy
- Obtain/review routine CT scans of the sinus. This information may be obtained through review of existing data

Day of Surgery

- Randomization into the Treatment Group or the Control Group, as per measures outlined in Section 6.2
- Scheduled routine surgical procedure previously planned, based on subject's condition
- Study intervention administration to all subjects
- Post-operative medication diary will be given to all subjects
- Post-operative visual analog pain scale will be given to all subjects
- Assessment of adverse events
- Assessment of concomitant medications

Post-Operative Clinic Visit #1 (Day 10-21)

- Obtain routine nasal endoscopy
- Review of medication diary
- Review of visual analog pain scale
- Pain medication reconciliation via pill count

- Assessment of adverse events
- Assessment of concomitant medication

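### Discharge opioid supply is neither fixed nor shielded from knowledge of the arm, so it could differ between arms and bias the pill-count measure of opioid use

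*Protocol*

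**What the plan says.** Section 4.1 states the design: "This is a Phase 4, randomized, single-blinded, single-site, parallel-assignment intervention". It does not say which party is blinded. All operations are "under the supervision of one surgeon". Section 4.3 says of the comparator, "The control group will receive no injection", and no section describes a sham.

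The day-of-surgery list in section 8.1 opens with "Randomization into the Treatment Group or the Control Group, as per measures outlined in Section 6.2", and the schedule in section 1.2 agrees. Section 6.2 adds only that the number and treatment "will only be allocated when entry of that subject to the randomized part of the trial has been confirmed". That ties allocation to trial entry, not to any prescribing step.

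Opioid use is the subject of the primary objective and, through a pill count at the first post-operative visit, the secondary endpoint (sections 1.1 and 3). Section 4.1 describes the method: "their opioid use will also be evaluated by counting the pills left on their prescription". A diary is kept alongside it. No section states the discharge opioid, its quantity, the refill policy, who writes the order, or whether that person knows the arm. Section 2.2 says that no guideline covers opioid prescribing after this operation, and cites a survey average of 27 pills.

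**The concern.** Use by pill count is the quantity dispensed minus the quantity left, so it cannot exceed what was dispensed. If treated patients leave with fewer pills, their measured use can be lower even when the injection has no effect. The diary does not remove the problem, because recorded use of the prescribed opioid has the same ceiling.

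The protocol already recognises that knowledge of the arm may affect opioid use through the patient. Section 4.2 says of controls who can still feel their face: "This could alert them to the fact that they were not injected with a local analgesic and thus reinforce the need for post-operative narcotic usage". It does not consider the same risk through the prescriber. Section 2.2 also expresses the hope that, with less pain, "we can theoretically decrease the number of opioid pain pills prescribed". That belief gives an unblinded prescriber a plausible reason to supply less after an injection.

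At stake is whether a difference in opioid use can be read as an effect of the injection. The order of allocation and prescribing is a matter of trial conduct, and an analysis plan cannot repair it afterwards.

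**Working it through.** **Is the route open in the text?**

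1. Allocation precedes discharge: sections 1.2 and 8.1 place it on the day of surgery.
2. Someone on the surgical side knows the arm: section 4.3 gives controls no injection, with no sham.
3. Supply is discretionary: no quantity, refill rule or blinded prescriber appears in any section.
4. The measure is bounded by supply: sections 1.1, 3, 4.1 and 6.3 rest on the pill count.

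The route is open. Two links are inferred: that the prescriber knows the arm, and that supply would respond to it.

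**How large could the effect be?** The plan has no figure of its own to reproduce; the sample-size section (9.2) is unfilled template text.

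Inputs from the protocol: 15 patients per arm (section 4.1), and 27 pills as the control supply (section 2.2, a survey average and not a trial rule). Assumed: pill need follows a gamma distribution that is the same in both arms; every treated patient receives 22, 20 or 15 pills; there are no refills; and the test is a two-sided t-test at 0.05.

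Measured use is min(N, S), for need N and supply S. With mean m and SD s, shape a = m²/s² and scale θ = s²/m,

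E[min(N, S)] = m·F(S; a+1, θ) + S·[1 − F(S; a, θ)],

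where F is the gamma distribution function. For m = 15 and s = 12, a = 225/144 = 1.5625 and θ = 144/15 = 9.6. This gives 13.45 pills at S = 27, 12.07 at S = 20 and 10.46 at S = 15. The false-rejection column is from 40,000 simulated trials per row.

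| Mean need (SD) | Supply, treated v control | Mean measured use, treated v control | Spurious change | False rejection |
|---|---|---|---|---|
| 10 (10) | 22 v 27 | 8.89 v 9.33 | −4.7% | 5% |
| 10 (10) | 20 v 27 | 8.65 v 9.33 | −7.3% | 5% |
| 10 (10) | 15 v 27 | 7.77 v 9.33 | −16.7% | 7% |
| 15 (12) | 22 v 27 | 12.55 v 13.45 | −6.6% | 6% |
| 15 (12) | 20 v 27 | 12.07 v 13.45 | −10.2% | 7% |
| 15 (12) | 15 v 27 | 10.46 v 13.45 | −22.2% | 19% |
| 20 (15) | 22 v 27 | 15.04 v 16.54 | −9.1% | 8% |
| 20 (15) | 20 v 27 | 14.29 v 16.54 | −13.6% | 12% |
| 20 (15) | 15 v 27 | 11.94 v 16.54 | −27.8% | 42% |

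Percentages use unrounded means. With 27 pills in both arms the spurious change is zero and false rejection is about 5%.

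**Second model.** Negative binomial need, 15 per arm, 20,000 trials. With mean 12 (SD 10), 15 against 27 pills gives a false difference of 2.0 pills and 11% rejection. With mean 18 (SD 12), the same supplies give 4.1 pills and 37%. Equal supply gives 0.0 pills and 4.9% to 5.2% rejection across the demand levels tried. The pattern is the same: the effect is small when few patients use up their pills, and large when many do and the supply gap is wide.

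**The case against.** The strongest reply is that the key step is inferred. No section says that the surgeon writes the discharge order, or that the order will depend on arm. The sentence in section 2.2 about fewer pills concerns future practice, and the text after it speaks of reaching a more uniform prescribing pattern. One supervising surgeon at one site also suggests a single habit. This stands in part: a reader might infer that treated patients will be given fewer pills, and the documents do not support that. A single habit is not a blinded one, though, so the possibility remains.

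A reader might also infer that any imbalance would be lost because the quantity dispensed is not recorded. The variable list in section 4.1 does name medication used and not dispensed. But a pill count yields use only if the starting number is known, section 6.3 reconciles the count with a medication log, and section 6.4 puts prescription medication in the case report form. The dispensed number is therefore probably known. Knowing it would reveal an imbalance without undoing it.

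Third, refills are not barred, so the first prescription need not be a ceiling. This stands and makes the table an upper illustration for the supplies assumed.

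Fourth, the formal primary endpoint is self-reported pain, which supply does not cap. This stands and limits the reach of the point, although the primary objective is worded in terms of opioid use.

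Finally, allowing changes to the order after allocation leaves the route partly open. That is true, but it preserves clinical freedom, and logging makes the changes visible.

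**Conclusion.** The point holds as a gap in protection against bias, not as a demonstrated bias. Supply could differ by arm through a prescriber who knows the allocation, and no section prevents it. What is exposed is the pill-count endpoint: formally secondary, but the subject of the primary objective.

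Under the assumptions above the spurious reduction runs from about 5% to 28%. At 15 per arm the false-positive rate usually moves little: 5% to 12% for supplies of 22 or 20 against 27. It ranges from 7% to 42% at 15 against 27, and is high only where many patients also use up their pills. Every need figure and every treated-arm supply is assumed; only 27 and the arm size come from the protocol. The change is worth making because it is cheap, not because a large distortion has been shown.

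**What to change.** Add to section 6.2 that the randomization number is opened only after the discharge opioid order, at the clinician's usual choice, has been entered in the source record. Alternatively, state that the person writing the order is unaware of the arm. Clinicians stay free to change the order at any time, and each change after allocation is logged with a reason. Name quantity dispensed and refills as case report form items, and report both by arm beside consumption so that any remaining imbalance can be seen. No quantity or prescribing rule is proposed.

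The cost is a sentence or two in section 6.2, a few data fields, and a small change in the order of steps on the day of surgery. It fits the existing day-of-surgery allocation. Changes after allocation remain possible, so the protection is incomplete, but they become visible.

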4.2 SCIENTIFIC RATIONALE FOR STUDY DESIGN

The rationale for our study deals with anesthetizing the sensory nerves of the face. The nerve distribution of the face deals with the trigeminal nerve. We plan to inject a long acting local analgesic at the infraorbital, infatrocchlear, external nasal, supraorbital, supratrochlear nerves of the face after functional endoscopic sinus surgery. The control arm will be randomly chosen for which patient will not be injected. A potential problem with the control group is that patients in the PACU will have intact facial sensation. This could alert them to the fact that they were not injected with a local analgesic and thus reinforce the need for post-operative narcotic usage.

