addition to systemic dose-related toxicity, unintentional subarachnoid injection of drug during the intended performance of caudal or lumbar epidural block or nerve blocks near the vertebral column (especially in the head and neck region) may result in underventilation or apnea ("Total or High Spinal"). Also, hypotension due to loss of sympathetic tone and respiratory paralysis or underventilation due to cephalad extension of the motor level of anesthesia may occur. This may lead to secondary cardiac arrest if untreated. Patients over 65 years, particularly those with hypertension, may be at increased risk for experiencing the hypotensive effects of bupivacaine hydrochloride. Factors influencing plasma protein binding, such as acidosis, systemic diseases which alter protein production, or competition of other drugs for protein binding sites, may diminish individual tolerance. Bupivacaine hydrochloride carries a black box warning for cardiac arrest with difficult resuscitation or death during use for epidural anesthesia in obstetrical patients.

- *Risks associated with dexamethasone sodium phosphate injection:* The most frequently reported adverse reactions are anaphylaxis, infection, seizures, hypertension, erythema, rash, urticarial, nausea, vomiting, edema, petechial, ecchymosis, skin pigmentation abnormality, acne, headache, dizziness, vertigo, insomnia, anxiety, and depression.
- *Risks associated with protocol-mandated procedures:*
 - *Surgical procedures:* All surgical procedures will be performed in the routine manner. There will be no additional clinical or surgical risks, other than the normal risks for patients undergoing this type of treatment.
 - *Questionnaires:* Completion of a questionnaire and the questions might make the subject feel uncomfortable or upset. Subjects will have the choice to not answer any such questions.

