3 OBJECTIVES AND ENDPOINTS

OBJECTIVES	ENDPOINTS	JUSTIFICATION FOR ENDPOINTS
Primary	Primary	Primary
The primary objective is to determine if a long-acting regional anesthetic applied after a surgery will reduce post-operative oral opioid usage.	The amount of post-operative pain after FESS. Participants will self-report a pain score on a scale of 0-10, with 0 being “no pain” and 10 being “worst pain imaginable.”	The use of narcotics post-operatively is to control pain; if we can reduce post-operative pain, essentially we can decrease post-operative opioid use.
Secondary	Secondary	Secondary
The secondary objective is to measure the level of each patient's pain.	Patients' daily pain medication usage. The amount of opioid medication used post-procedure will be determined by a pill count at the first post-operative clinic visit.	Pain is a subjectively based outcome that can be difficult to determine prior to a surgery. We believe if we are able to reduce pain in the majority of our patients tested then, we can apply this on a global scale to create a uniform number of opioid pain medications prescribed after surgery.

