6.1.2 DOSING AND ADMINISTRATION

Treatment Group: 20 mL of 1.3% bupivacaine with 2 mg dexamethasone injected locally in the location for sensory nerves of the sinus cavities and face during the FESS.

Control Group: No local regional anesthetic will be used during the FESS..

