7.2 PARTICIPANT DISCONTINUATION/WITHDRAWAL FROM THE STUDY

Participants are free to withdraw from participation in the study at any time upon request.

An investigator may discontinue or withdraw a participant from the study for the following reasons:

- If any clinical adverse event (AE), laboratory abnormality, or other medical condition or situation occurs such that continued participation in the study would not be in the best interest of the participant
- Disease progression which requires discontinuation of the study intervention
- If the participant meets an exclusion criterion (either newly developed or not previously recognized) that precludes further study participation
- Non-compliance with follow-up activities

Subjects who sign the informed consent form and are randomized but do not receive the study intervention may be replaced. Subjects who sign the informed consent form, and are randomized and receive the study intervention, and subsequently withdraw, or are withdrawn or discontinued from the study, will be replaced.

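### Randomization is listed ahead of the operation and nothing keeps the arm from the operator until the injection, although the arm is not needed before then

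*Protocol*

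**What the plan says.** **Order of events.** The day-of-surgery list in section 8.1 opens with "Randomization into the Treatment Group or the Control Group, as per measures outlined in Section 6.2". The operation comes next and the intervention third. The narrative in section 4.1 also has randomization before the operation. The Schedule of Activities (1.2) fixes only the day. Section 6.2 releases the next number once the subject's entry to the randomized part is confirmed, and does not tie that confirmation to any point in the operation.

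**Timing of the injection.** Section 4.2 describes injecting nerves including the "supratrochlear nerves of the face after functional endoscopic sinus surgery". The primary objective in section 3 is to "determine if a long-acting regional anesthetic applied after a surgery will reduce post-operative oral opioid usage". The arm definition in 4.1 has the drug "injected locally in the location for sensory nerves of the sinus cavities and face during the FESS procedure", and section 6.1.2 and the intervention description in 1.1 agree with that.

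**Who knows the arm.** Section 4.1 describes a single-blind trial under one supervising surgeon and does not name the blinded party. Section 4.3 gives controls no injection, and no sham is described.

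**Operative conduct.** Section 2.3.1 says: "All surgical procedures will be performed in the routine manner". Section 8.1 describes the operation as planned in advance. Packing appears only in the background (2.2), which reports of earlier work that "adding non absorbable sinus packs loaded with local anesthetics such as bupivacaine achieved less pain values and improved patient satisfaction scores". The variable list in 4.1 includes type and duration of surgery but not packing.

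**Losses after the draw.** Section 7.2 states: "Subjects who sign the informed consent form and are randomized but do not receive the study intervention may be replaced". Section 7.1 labels subjects discontinued from the intervention as screen failures and removes them from the dataset. Section 5.3 reserves that term for people who consented but were not randomized or entered.

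**The concern.** The arm is needed only when the injection is given or withheld. Drawing it earlier has two avoidable consequences.

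First, it opens a route to performance bias. With no sham, the person who injects must know the arm. If that knowledge is available from the start of the case, any discretionary decision before the injection that affects later pain could differ between arms for reasons unrelated to the block. Pain is the primary endpoint, and a comparison of 15 with 15 has little room to absorb such a difference.

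Second, it lengthens the period in which a randomized subject can drop out before the injection point. A case cancelled or changed in that period is a post-randomization loss. Had the draw come later, the same case would never have been randomized.

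Both are matters of trial conduct. An analysis plan cannot restore concealment that was not kept, or recover data removed by rule.

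**Working it through.** The protocol states no figure on this point, so there is none to reproduce. The check sets the passages side by side.

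**1. Is the draw placed before the operation?** The sequences in 8.1 and 4.1 agree, and no passage says otherwise. The evidence is the order of the text, since 1.2 gives only the day and no section gives a clock time.

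**2. Does any rule defer it?** Section 6.2 is the only release rule. Its condition, confirmed entry to the randomized part, can be met before the operation starts. It permits a late draw but does not require one.

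**3. Is the arm needed earlier than the injection?** Both arms have the operation already scheduled and differ only in the injection. So the arm is not needed earlier, whether the injection comes during or after the operation.

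**4. Is the arm hidden from the operator until then?** No passage does so. Nor does any passage say when the operator is told.

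**5. What happens to subjects lost in between?**

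| Section | Rule |
|---|---|
| 5.3 | Screen failure means consented but not randomized or entered |
| 7.1 | Discontinued from the intervention: called a screen failure, data removed |
| 7.2 | Randomized but not treated: may be replaced |

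Section 7.2 allows replacement and does not itself remove data. Removal comes from 7.1, and only if a subject who was never injected is counted as discontinued from the intervention, which the protocol does not settle. The protocol gives no loss rate. By arithmetic, each subject removed is 1/15 = 6.7% of an arm, or 1/30 = 3.3% of the trial.

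**6. Illustration of the bias route.** All effect sizes and frequencies here are assumptions with no source in the protocol. Inputs: 15 per arm (4.1), two-sample t-test, two-sided 5%, 28 degrees of freedom, noncentrality = d × √(15/2), where d is the contrast in SD units.

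*Dilution.* Assume a true block effect of 1.0 SD. A fraction q of controls receives a co-intervention worth a fraction r of that effect, so the contrast is 1 − q × r.

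| q | r | Contrast (SD) | Power |
|---|---|---|---|
| 0 | – | 1.00 | 0.753 |
| 0.2 | 0.5 | 1 − 0.10 = 0.90 | 0.663 |
| 0.4 | 0.8 | 1 − 0.32 = 0.68 | 0.436 |

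*False difference.* Assume no block effect, and a co-intervention worth 0.8 SD used in 20 to 40 percentage points more of the treatment arm.

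| Imbalance | False contrast (SD) | Rejection rate |
|---|---|---|
| 0 | 0 | 5% |
| 0.2 | 0.2 × 0.8 = 0.16 | 7.1% |
| 0.4 | 0.4 × 0.8 = 0.32 | 13.5% |

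These rows show how sensitive a trial of this size would be if such an imbalance arose. They do not show that it would.

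**The case against.** The strongest reply is that the harm is inferred. A reader might conclude that the operator chooses packing and surgical extent knowing the arm. The documents do not support that. They do not say when the operator learns the arm, they call the operation planned in advance and routine, and they mention packing only in the background, for packs loaded with anesthetic. No passage says that packs of any kind are used in this trial, and section 6.1.2 excludes local regional anesthetic from the control arm. This stands: the bias is a possibility left open, and the power and error figures above are not properties of this protocol.

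A reader might also infer that early randomization spoils type and duration of surgery as covariates. Planned type is known before randomization in any case, no covariate is specified, and the analysis plan is not at hand. What remains is narrower: operative values are certain to be free of the arm only if they are fixed before it is revealed.

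It can further be said that the removal rule in 7.1 is a fault of its own, which a later draw would not cure. That is right. Subjects withdrawn after the injection would still be replaced under 7.2. A later draw only shortens the period of exposure.

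Finally, list order is weak evidence of sequence. Section 8.1 puts the intervention after the operation, while the arm definitions put it during. If the injection is given during the operation, the gap is shorter and some decisions follow it anyway. Even so, two sections give the same order for the draw and none requires a later one.

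**Conclusion.** The point holds as a design weakness that should be corrected. The protocol lists randomization ahead of the operation and does not keep the arm from the operator until the injection. Decisions made before the injection could therefore be taken with the arm known, and subjects lost in between may be replaced or, under one reading of 7.1, dropped from the data.

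The conclusion rests on the order given in 4.1 and 8.1, the absence of any deferral in 6.2, and a control arm with no sham. It does not depend on whether the injection is given during or after the operation, or on packs being used.

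Its size cannot be estimated from the protocol, which gives no loss rate, effect size or packing frequency. The only figure that follows directly is 6.7% of an arm for each subject removed.

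**What to change.** **Randomization.** In 1.2, 6.2 and 8.1, state that a staff member already present, other than the operator, opens the next allocation immediately before the injection is due, and that this is when entry to the randomized part is confirmed. This wording works under either reading of the injection timing.

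**Recording.** Require that operative decisions made up to that point (procedures performed and, if used, packing) are written down before the allocation is opened. Add a packing field to the variable list in 4.1. Values recorded before the reveal are then pre-randomization and can be used for adjustment. Total duration of surgery qualifies only if the operation is over by then.

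**Losses.** A case that stops before the reveal then falls properly under the screen-failure definition in 5.3. Reconcile 7.1 with 5.3 so that no randomized subject is relabelled as a screen failure, and keep all randomized subjects in the analysis.

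**For the sponsor to settle.** The passages that put the injection during the operation (intervention description in 1.1, arm definitions in 4.1, 6.1.2) and after it (primary objective in 3, 4.2) must be reconciled. Sections 1.1 and 4.1 are also divided within themselves, since each repeats the objective with the later timing. No view is taken here on which is right. Any packing policy is a clinical decision and should apply equally to both arms.

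**Cost.** Protocol wording, one data field, a brief step in theatre and study drug prepared at short notice. No extra patients or study visits. Decisions made after the reveal remain open to knowledge of the arm.
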